The present non-interventional study will aim to provide a Europe-wide picture of (i) the demographic and clinical features of HFrEF patients managed in the outpatient sector and the diagnostic and pharmacologic intervention they receive; (ii) the demographic and clinical features of patients the treating physician decided to start sacubitril/valsartan, the pattern of administration of this drug, the diagnostic and therapeutic intervention these patients receive and the safety and tolerability profile of this drug in real life.

Main objectives:

- To describe the profile of patients initiated on sacubitril/valsartan and patients continued on SoC in the outpatient sector in terms of demographics, medical history, HF status, comorbidity burden
- To describe the profile of sacubitril/valsartan patients not reaching and maintaining the target dose of 200 mg twice daily in terms of demographics, medical history, HF status, comorbidity burden as compared with patients reaching the target dose

Additional objectives:

- To describe the overall HFrEF population managed in the outpatient sector in Europe in terms of demographics, medical history, comorbidity burden and previous cardiovascular (CV) events rate
- To describe HF-treatment (pharmacological and non-pharmacological) in the outpatient sector in Europe and in individual countries/country clusters
- To describe the starting dose, titration and maintenance dose of sacubitril/valsartan in patients with different anamnestic and demographic characteristics
- To assess the rates of major HF related outcomes (death, hospitalizations, major CV events)
- To describe Healthcare Resource Utilization in HFrEF patients managed in the European routine practice
- To describe safety and tolerability features of sacubitril/valsartan in real-world HF patients
- To describe the quality of life (QoL) during follow-up (only in those sites where the EQ-5D and/or KCCQ QoL questionnaires are part of routine CHF management)
- To describe the levels of BNP / NT-proBNP (only if these measurements are available or at sites where these measurements are performed within the routine CHF management)

7 Research methods

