Note: The decision to treat a patient with individualized currently available therapies (SoC) or to start sacubitril/valsartan is to be taken by each investigator according to his/her clinical judgment and independently form participation in this study. Only after that decision is taken, the patient will be enrolled, in order to respect and describe real world clinical practice.

Every effort will be made to reduce selection bias by enrolling patients on a consecutive basis. This also means that patients, who already have been initiated on sacubitril/valsartan treatment after the drug has become commercially available can be included into the study, if they satisfy all inclusion and exclusion criteria and the investigator has the sufficient baseline information (see Section 7.3) on file for these patients.

Follow-up for all patients will last up to 12 months after the baseline visit. The follow-up will consist of 2 visits closest to 6 months and 12 months after the baseline visit, respectively (recommended visit window of \pm 2 months). No exact date for the second and final visits will be enforced, to avoid interference with the real life routine care. In case intermediate visit (6 month) will not take place, this will be recorded and described as part of real world practice.

At any time during the study, the investigator is free to adapt or change the patient's CHF treatment as per his/her clinical judgement at any time – the reasons for switching treatments as well as specific details of the new CHF treatment will be documented. The duration of the patient's follow-up is not altered by the switching of therapy, i.e. the individual follow-up duration is only dependent on the time point of the enrollment.

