7.2.3 Exclusion criteria

- 1. Concomitant or planned participation in any interventional clinical trial
- 2. Patients who are receiving ongoing treatment with sacubitril/valsartan that has been started prior to market launch in their respective country, e.g. within a clinical trial or early access program.
- 3. Patient still within the safety follow up phase of any previous interventional or non-interventional trial using sacubitril/valsartan (LCZ696), independently whether they received sacubitril/valsartan or the comparator.
- 4. Acute decompensated HF requiring hospitalization at the moment of enrollment.
- 5. Existing contraindications according to approved product information

No additional restrictions for inclusion or exclusion are provided in order to ensure that the patients enrolled are as close as possible to (i.e. representative of) the real population of CHF patients with reduced LVEF managed in the office-based setting.

Page 21

7.3 **Variables**

- Demographics (age, gender, living at home or institution, relationship status, education)
- Medical history and comorbidity burden (with focus on duration of HF, etiology of CHF, last hospitalization for HF, cardiovascular conditions, specific comorbidities such as diabetes, renal insufficiency, COPD, anemia, obesity, cancer)
- Clinical Events (both retrospectively over the past 12 months and prospectively, as applicable):
 - Death (CV related and non-CV related, only prospectively)
 - Hospitalizations (defined as at least one overnight staying): number, elective or not, reason for hospitalization (CV related, HF related, non CV related)
 - **Myocardial Infarction**
 - Stroke
- Number of visits (other than hospitalization) by provider and primary reason during follow-up:
 - Emergency room/department
 - Outpatients office visits (general practitioner; cardiologist; internist; other specialist)
 - Cardiology (day) clinic
 - Device clinic
 - Nurse services/ day clinic
 - Rehabilitation facilities
- Diagnostic and therapeutic procedures utilized during follow-up (Results will be collected only as available for blood potassium, blood creatinine, BNP, NT-proBNP and for echocardiographic EF. In all other cases, the eCRF will only capture if the procedure has been performed and its primary reason)
 - Echocardiogram (LVEF in % if available)
 - ECG / stress ECG
 - Chest X ray
 - Pulmonary function tests
 - Computed Tomography of the Heart
 - Cardiac Magnetic Resonance Imaging
 - Cardiac catheterization

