7.9 Limitations of the research methods

Potential limitations of the present study are due to its non-interventional character, where no stipulation regarding data collection can be made. In the present study, not all involved sites use QoL questionnaires or certain lab parameters within the routine management of CHF and thus, these data will not be available for all patients. In addition, there is no randomization or blinding within a NIS; especially QoL data from non-blinded patients need to be interpreted carefully. However, the non-interventional character of the study is the only way to obtain real-life data. In order to obtain a representative sample of the population of CHF patients from the outpatient sector, the ARIADNE NIS will not mandate diagnostic nor therapeutic processes which would distort the recruitment.

However, non-cardiac disorders as well as HFpEF (HF with preserved systolic function) can be confused with HFrEF. In order to ensure sufficient homogeneity of the patient population, inclusion will require that the patient has documentation of reduced left ventricular systolic function (LVEF) in the past through any imaging technique.

To reduce the selection bias in the patients an investigator will include into the NIS, the physician is urged to offer enrollment to all consecutive patients and not select patients from his patient database. However compliance with this requirement cannot be verified due to data privacy regulations; therefore the investigators are asked to diligently follow the good epidemiological practice requirement of offering participation to this study to consecutive patients.

A potential selection bias might arise from the bi-phasic enrollment of SoC patients. This risk is mitigated by following design features:

- there is no minimal time requirement for the patient being on SoC prior to enrollment into the study and
- patients can be switched to the optimal therapy as per judgement of the investigator at any time of the study.

Thus, there is no incentive for increased prescribing (and therefore for a selection bias) sacubitril/valsartan during phase 2 of enrollment (when enrollment into the SoC group is paused). If a patient is receiving SoC during enrollment phase 2 and still would like to participate in the NIS when enrollment into this group is commenced again (i.e. phase 3) he/she can be enrolled into the SoC group at that time, as there are no temporal stipulations regarding duration of SoC treatment.

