Serious adverse event with causal relationship to respective treatment (i.e. SADR)	 Report to local health authority as per local regulations. In case Novartis drug, additionally report to Novartis DS&E as spontaneous report 	 Report to Novartis DS&E within 24h of awareness; to local health authority will be performed by Novartis DS&E Enter within 24h into eCRF

An adverse event is any untoward medical occurrence in a patient participating in this study (after signing the ICF) that does not necessarily have a causal relationship with the treatment.

An AE can therefore be any unfavorable and unintended sign (including an abnormal laboratory finding), symptom, or disease temporally associated with the use of a drug of interest, whether or not related to the medicinal product(s).

Drug of interest is the drug under evaluation (sacubitril/valsartan) given at any time during the study. Medical conditions/diseases present before the Baseline visit are only considered adverse events if they worsen after start of study (Baseline visit).

The occurrence of adverse events should be sought by non-directive questioning of the patient at each visit during the study. Adverse events may also be detected when they are volunteered by the patient during or between visits or through physical examination, laboratory test, or other assessments.

Abnormal laboratory data or test results should only be documented as adverse events if:

• There is a change in terms of a worsening of respective parameters compared to the baseline (baseline visit). This requirement is not applicable if there is no previous baseline value.

AND

• Altered lab parameters

- Are classified as clinical relevant OR
- Come along with clinical signs and symptoms OR
- Indicate a therapeutic intervention OR
- Lead to a dose reduction and / or temporary interruption or permanent discontinuation of the investigational drug in the NIS

In such cases they must be documented as AEs. Changes of a quantifiable parameter must be documented as SAE in the following cases, if:

- Formal criteria of SAE are met (see definition SAE)
- It exceeds or falls below the pre-determined limit for the respective parameter

Adverse event reporting

All adverse events occurring **in patients taking sacubitril/valsartan** (see Table 9-1) must be recorded on the Adverse Events eCRF containing the following information:

- 1. the severity grade (mild, moderate, severe)

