Note: A *progression of the underlying disease* while receiving treatment with the drug studied in this NIS can be documented as an adverse event (AE) only if a causal connection with the treatment with the drug studied in this NIS is suspected, or if as a result of disease progression one or more of the formal criteria for a serious adverse event (SAE) listed under the SAE definition is/are met.

SAE reporting

To ensure patient safety, every SAE in patients taking sacubitril/valsartan (see Table 9-1), regardless of causality assessment, occurring after the patient has provided informed consent and until 30 days after the patient has stopped study participation (defined as time of last dose of the Novartis drug of interest taken or last visit whichever is later) must be reported to Novartis within 24 hours of learning of its occurrence (see below).

Any SAEs reported more than 30 days after study termination should only be reported to Novartis if the treating physician or other involved health care professional suspects a causal relationship to the Novartis drug of interest.

Recurrent episodes, complications, or progression of the initial SAE must be reported as follow-up to the original episode, regardless of when the event occurs. This report must be submitted within 24 hours of the treating physician or other involved health care professional receiving the follow-up information. An SAE that is considered completely unrelated to a previously reported one should be reported separately as a new event.

Information about all SAEs in patients taking sacubitril/valsartan is collected and recorded on the Serious Adverse Event eCRF – this information needs to be entered into the eCRF within 24 hours of awareness. Depending on local reporting requirements, there may be two ways of submitting the SAE information to Novartis DS&E:

• Paper SAE Form: Information about all SAEs is collected and recorded on the Serious Adverse Event Report Form. The treating physician or other involved health care professional must assess the relationship to the Novartis drug of interest, complete the SAE Report Form and send the completed, signed form by fax within 24 hours to the local Novartis Drug Safety & Epidemiology (DS&E) Department. The telephone and telefax number of the contact persons in the local department of DS&E, specific to the site, are listed in the treating physician or other involved health care professional folder provided

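### The sacubitril/valsartan group pools new starters with patients already on the drug, so pre-consent adverse events and patients who stopped or died before enrollment are missing from it

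*Protocol*

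**What the plan says.** **Entry.** Section 7.2.1 presents the admission of current users as part of consecutive enrollment: "patients, who already have been initiated on sacubitril/valsartan treatment after the drug has become commercially available can be included into the study", provided they meet the criteria and enough baseline information is on file. No limit is set on how long ago treatment began. The exclusion for current use in Section 7.2.3 covers only "Patients who are receiving ongoing treatment with sacubitril/valsartan that has been started prior to market launch in their respective country". Nothing there addresses a patient who tried the drug after launch and stopped, and the section adds that "No additional restrictions for inclusion or exclusion are provided".

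**Group and clock.** Section 7.1 keeps each patient in the group given by treatment at enrollment. Follow-up runs from the baseline visit (7.2.1). The second main objective is judged within the 12-month observation period (7.1, 7.5).

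**Safety.** Section 9 defines the event from consent onwards: "An adverse event is any untoward medical occurrence in a patient participating in this study (after signing the ICF"). It adds: "Medical conditions/diseases present before the Baseline visit are only considered adverse events if they worsen after start of study (Baseline visit"). SAE reporting likewise covers events "occurring after the patient has provided informed consent".

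**SoC group.** Section 7.9 says that "there is no minimal time requirement for the patient being on SoC prior to enrollment into the study".

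**Objective.** The first main objective in Section 6 is: "To describe the profile of patients initiated on sacubitril/valsartan and patients continued on SoC in the outpatient sector". Section 7.7 describes the sacubitril/valsartan group as receiving a newly prescribed therapy.

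**The concern.** These rules together produce left truncation. Someone already on the drug at enrollment has, by construction, survived and tolerated it for long enough to be there. Someone who began treatment on the same day but stopped or died before the enrollment visit is not in the sacubitril/valsartan group. An adverse event that an already-treated member had before consent is not counted, and a reaction still present at baseline counts only if it gets worse.

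The results exposed are the proportion and profile of patients who do not reach and maintain the target dose (second main objective), the titration description and the adverse event incidence. The expected direction is towards better apparent tolerability. The first main objective is touched as well: an early stopper may be enrolled as SoC and then be described among patients continued on SoC. Section 7.9 discusses bi-phasic SoC enrollment and the absence of a time rule for SoC, but not the pooling of new and established users. A larger sample narrows the interval without removing this bias.

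**Working it through.** **1. The plan's own figures (Section 7.5).** These reproduce.
- Proportion, n = 6000: 1.96 × √(0.25/6000) = 1.265 points. Stated: ±1.3.
- Proportion, n = 3000: 1.96 × √(0.25/3000) = 1.789 points. Stated: ±1.8.
- Target-dose failures: 6000 × 0.50 = 3000, as stated. At the 23.8% seen in the cited titration trial: 6000 × 0.238 = 1428.

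**2. Inputs for the truncation check.**
- F, true failure rate among all starters: 50% (planning value) or 23.8% (cited trial), both from Section 7.5.
- f, share of the sacubitril/valsartan group already on drug at enrollment: not in the protocol; assumed 10-50%.
- s, share of failures who stop before the enrollment visit: not in the protocol; assumed 10-50%.
- Apart from truncation, already-treated patients are assumed to have the same failure risk as new starters.

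**3. Formulas.**
- Failure rate among already-treated patients: F(1 − s)/(1 − F·s).
- Rate observed in the pooled group: (1 − f)·F + f·F(1 − s)/(1 − F·s).

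Worked example, F = 0.50, s = f = 0.25: already-treated rate 0.375/0.875 = 0.4286; pooled rate 0.75 × 0.50 + 0.25 × 0.4286 = 0.4821; understatement 1.8 points.

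**4. Understatement of the failure rate, in percentage points.**

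| True rate | s | f = 10% | f = 25% | f = 50% |
|---|---|---|---|---|
| 50% | 10% | 0.3 | 0.7 | 1.3 |
| 50% | 25% | 0.7 | 1.8 | 3.6 |
| 50% | 50% | 1.7 | 4.2 | 8.3 |
| 23.8% | 10% | 0.2 | 0.5 | 0.9 |
| 23.8% | 25% | 0.5 | 1.2 | 2.4 |
| 23.8% | 50% | 1.0 | 2.6 | 5.1 |

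The observed rate runs from 49.7% down to 41.7% for a true 50% (2984 down to 2500 failures instead of 3000). For a true 23.8% it runs from 23.6% down to 18.7% (1417 down to 1119 instead of 1428). The 95% half-width for these pooled rates is about 1.3 points near 50% and 1.0 to 1.1 points near 23.8%, so the bias is below sampling error in part of the grid and well above it elsewhere.

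**5. Possible spill into SoC.** The number of early stoppers behind the already-treated patients is 6000·f × F·s/(1 − F·s). The smallest case (F = 0.238, s = f = 0.10) is 600 × 0.0238/0.9762 = 15. The largest (F = s = f = 0.50) is 3000 × 0.25/0.75 = 1000. If every one of them entered as SoC, which is an upper bound, they would fill 0.2% to 16.7% of 6000 places.

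**The case against.** A reader might infer that everything before consent is lost. The protocol does not support that. For patients still on the drug, Section 7.3 records dose at initiation, titration steps and the reason for failing to up-titrate, reducing or stopping. A patient who entered below target and stays there is still a failure during follow-up. Hospitalization, infarction and stroke in the previous 12 months are collected, as is HF treatment in the previous 6 months, so a recent stopper enrolled as SoC should be identifiable. What these data cannot do is recover pre-consent adverse events or return early stoppers and early deaths to the denominator. Use that ended more than 6 months before baseline need not be recorded at all.

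A reader might also infer a bias of several points. That needs a large already-treated share and much early stopping. Section 7.2.1 expects slow uptake, with enrollment starting in each country when the drug becomes available, and Section 7.5 frames failure as lack of up-titration, which often leaves the patient on the drug. The low end of the grid is therefore plausible. Nor is the direction certain in every patient: one who held the target dose before consent and was reduced soon after baseline could count as a failure, because the assessment runs over the observation period.

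The design is also reasoned and partly disclosed. Admitting current users follows from consecutive enrollment. Section 7.9 names missing time and prior-treatment rules as limitations to be handled by stratification, and Section 7.7 lists previous HF treatment as a stratifier. It also plans no follow-up or safety comparison between groups, and says that SoC is continued only in most cases. Patients with existing contraindications are excluded from either group. All of this stands and lowers the severity. Section 7.7 leaves analysis populations to the SAP, which is not at hand. But the entry rule and the start of event counting are fixed in the protocol, and among the strata it does name (enrollment phase, treatment group, switching) new versus established users does not appear.

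**Conclusion.** The concern holds as a should-fix. As written, the protocol mixes new starters with a left-truncated set of established users, and counts adverse events only from consent. Early intolerance and target-dose failure therefore tend to be understated in the sacubitril/valsartan group, and some early stoppers may be described as SoC, at odds with the contrast between initiated and continued patients in Section 6.

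The size is not derivable from the protocol. Under the assumed ranges for f and s, the bias in the failure rate is about 0.3 to 8.3 points at a true 50% and 0.2 to 5.1 points at 23.8%. With both inputs at 25% it is 1.8 and 1.2 points, slightly more than the sampling half-widths of 1.3 and 1.1 points. The calculation covers a proportion only. It does not show how far the descriptive profiles would move, and it puts no figure on adverse events.

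**What to change.** - **Data (7.3):** record the date of first sacubitril/valsartan dose for every patient who has received it, if the eCRF does not already hold it.
- **Analysis (7.7):** report target-dose attainment, titration pattern and adverse event incidence primarily in new starters, meaning first dose at baseline or within a short window before it that is fixed in advance. Show already-treated patients as a separate stratum.
- **SoC group (7.7):** use the prior HF treatment already collected to flag SoC patients with sacubitril/valsartan use in the 6 months before baseline, and show them separately from the rest.
- **Limitations (7.9):** state that pre-consent adverse events and patients who stopped or died before enrollment are missing from the sacubitril/valsartan group, with the likely direction.

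The cost is at most one eCRF field plus protocol and SAP wording; no extra patients or visits are needed. The new-starter analyses lose precision. If 10-50% of the 6000 are already treated, 5400 to 3000 new starters remain, and the half-width for a proportion is at most 1.96 × √(0.25/5400) = 1.3 points to 1.96 × √(0.25/3000) = 1.8 points.

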7.1 Study design

This is an observational, European NIS with prospective collection of primary data. Data will be collected for two groups of HFrEF patients: Patients who receive individualized SoC and patients for whom the physician has decided to prescribe sacubitril/valsartan. If the patient is to be started on sacubitril/valsartan, the decision to prescribe sacubitril/valsartan has to be made independently from the participation in this study. This independency is ensured by the fact that patients with any CHF treatment, who satisfy the inclusion and exclusion criteria, can be enrolled. The treating physician can adapt the CHF treatment during the follow-up phase of the study according to his/her decision. The patients will be followed up over 12 months after enrollment, independently whether they remain on the same CHF treatment they received at the time of enrollment, or are switched to another CHF treatment (see Section 7.2). If during the follow-up phase patients are switched from SoC to sacubitril/valsartan or *vice versa*, they will remain nominally allocated to their original group (i.e. based on their treatment at the time point of enrollment). Details on the analysis of different CHF treatment populations will be provided in the statistical analysis plan.

The main objective of the study is to describe the profiles of symptomatic CHF patients who are prescribed sacubitril/valsartan or SoC in terms of demographics, medical history, HF status, comorbidity burden at the time point of the baseline visit.

A co-primary objective is to describe the profiles of symptomatic CHF patients who are prescribed sacubitril/valsartan and do not achieve and maintain the target dose of 200 mg BID within the observation period of 12 months in terms of demographics, medical history, HF status, comorbidity burden.

The **endpoints yielding to the primary objectives** are descriptive in nature and will be derived from the baseline demographic and medical history variables and sacubitril/valsartan treatment data (see Section 7.3).

Additional endpoints:

- Number of patients achieving a target sacubitril/valsartan dose of 200 mg BID
- Number of patients maintaining the target dose of sacubitril/valsartan 200 mg BID
- Description of SoC treatments (drug and non-drug) according to each participating country (e.g. drug, daily dose).
- Incidence of major CV events and adverse events (AE)
- Change in NYHA status

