7.2 Setting

7.2.1 Population

The present study will include consecutive HFrEF patients treated by office-based cardiologists or selected primary care physicians (recognized as HF specialists) across Europe.

The study will include overall 6000 patients on SoC and 6000 patients on sacubitril/valsartan.

Considering that the different local regulations on patient management and reimbursement can significantly impact clinical practice, patient numbers will be allocated to bigger countries and/or clusters of smaller countries with similar healthcare systems in order to ensure the representativeness of the sample.

Enrollment will start in each country when sacubitril/valsartan is available for clinical use. Assuming that the penetration of sacubitril/valsartan into clinical practice will be slow immediately after launch, the enrollment of sacubitril/valsartan patients will take a significantly longer time than including SoC patients. At each country level the enrollment of sacubitril/valsartan patients will be continuous, while the enrollment of SoC patients will be divided into two phases, where approximately one half is immediately enrolled at the start of the study and the other half is enrolled during the last part of enrollment into the sacubitril/valsartan group (see Figure 7-1). By structuring the enrollment of SoC patients in this two-wave pattern, the possibility is created to compare the baseline demographic and medical characteristics of patients that drive the choice of physicians toward individualized SoC or sacubitril/valsartan (main objective) and see if their approach changes over time, after the launch of sacubitril/valsartan.

LCZ696 launch in Country A ~ 50 % ~ 50 % SoC SoC 100% LCZ696 Phase 2 Phase 1 Phase 3 12 months В ~ 50 % ~ 50 % LCZ696 launch in Country SoC SoC 100% LCZ696 Phase 1 Phase 2 Phase 3 12 months S ~50 % ~ 50 % LCZ696 launch in Country SoC 100% LCZ696 Phase 1 Phase 2 Phase 3

Figure 7-1 Enrollment schedules (examples) on single country level

Overall enrollment: 24 months

Enrollment schedule for each country will depend on enrollment numbers in SoC and sacubitril/valsartan groups and thus might need to be divided into phases, where SoC enrollment is split up in two phases, while LCZ696 enrollment is continuous (examples A-C). SoC = standard of care, LCZ696 = sacubitril/valsartan

12 months

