7.2.2 Inclusion criteria

- 1. Written informed consent provided by the patient or legal representative for participating in the study (according to country specifications).
- 2. Age \geq 18 years.
- 3. Patients with symptomatic CHF (NYHA class II IV) with a documented reduced left ventricular ejection fraction (LVEF) as assessed by clinical examination and any imaging technique performed anytime in the past.

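### No index date is fixed for the baseline profile of patients already taking sacubitril/valsartan at enrollment, yet that profile is read as what led to the prescribing decision

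*Protocol*

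**What the plan says.** - **Who may enter (Protocol 7.2.1).** As part of consecutive enrollment, "patients, who already have been initiated on sacubitril/valsartan treatment after the drug has become commercially available can be included into the study". The condition is that they qualify "if they satisfy all inclusion and exclusion criteria and the investigator has the sufficient baseline information (see Section 7.3) on file for these patients". No maximum time since first dose is given. Exclusion criterion 2 (7.2.3) bars only treatment begun before market launch.
- **When the profile is taken (7.1).** The main objective describes patients "in terms of demographics, medical history, HF status, comorbidity burden at the time point of the baseline visit". Section 9 equates the baseline visit with the start of the study, and Section 7.2.1 runs follow-up from enrollment.
- **How the profile is used (7.2.1, 7.7).** The two-wave enrollment is meant to make it possible to "compare the baseline demographic and medical characteristics of patients that drive the choice of physicians toward individualized SoC or sacubitril/valsartan". Section 7.7 disclaims inference from comparing the two groups except for the baseline characteristics that led to the decision.
- **Symptom criterion (7.2.2).** "Patients with symptomatic CHF (NYHA class II IV) with a documented reduced left ventricular ejection fraction" carries no date for NYHA class and no provision for patients already treated. The look into the past concerns imaging. Section 7.9 confirms this: "inclusion will require that the patient has documentation of reduced left ventricular systolic function (LVEF) in the past through any imaging technique".

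**The concern.** For a new starter, the treatment decision and the baseline visit roughly coincide. For a patient who has been taking the drug for weeks or months they do not. A value measured after the decision cannot have contributed to it. If the baseline visit is the index date, the sacubitril/valsartan group mixes two kinds of patient: new starters described before treatment, and already-treated patients described under it. The between-group description of baseline characteristics is the one comparison from which Section 7.7 keeps an inference, so the mixing falls on the first main objective. Summaries of change in NYHA class and in BNP/NT-proBNP would also start from different points within one group. The undated NYHA criterion adds a second question: whether a patient who was symptomatic at first dose but is in class I at enrollment qualifies.

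**Working it through.** **1. The index date, place by place**

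| Protocol section | What it implies for a patient already on drug |
|---|---|
| 7.2.1, entry condition | Baseline information is on file; this can mean records from before first dose |
| 7.1 and 9 | Profile at the baseline visit, which is the start of study |
| 7.2.1 and 7.7, use | Characteristics that preceded and led to the decision |
| 7.2.2, criterion 3 | NYHA class at an unstated date |
| Table 7-1 | Baseline, 6 and 12 months; no pre-dose column |

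Neither reading satisfies every row. If the index date is before first dose, it conflicts with 7.1 and 9, and Table 7-1 has no place for the values. If it is the baseline visit, the values postdate the decision that 7.2.1 and 7.7 use them to explain.

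**2. Which variables are affected (7.3)**

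- Little affected: age, sex, education, etiology and most of the medical history.
- On-treatment if taken at the visit: NYHA class, blood pressure, pulse, HF signs and symptoms, potassium, creatinine, BNP/NT-proBNP.
- Partly affected: the 12-month event look-back. For a patient t months after first dose, a share t/12 of the window is on drug. For example, t = 3 gives 3/12 = 25%. The whole window is on drug only when t is at least 12.
- Prior HF treatment is required only if ongoing or changed in the last 6 months (7.3 and the Table 7-1 footnote). The therapy that preceded a start more than 6 months ago therefore need not be recorded, although 7.7 stratifies by previous HF treatment.

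**3. The plan's own precision (7.5)**

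Half-width for a proportion at p = 0.5 is 1.96 × √(0.25/n); for a mean it is 1.96 × SD/√n.

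- n = 6000: 1.265 points (stated ±1.3) and 0.0253 SD (stated ±0.025).
- n = 3000: 1.789 points (stated ±1.8) and 0.0358 SD (stated ±0.036).

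The stated figures are reproduced up to rounding. They give a yardstick for bias.

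**4. Size of the mixing bias**

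Let f be the already-treated share of the sacubitril/valsartan group, and d the percentage-point shift of a characteristic on treatment. The bias in the group proportion is f × d. The documents give neither, so the values below are assumptions.

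| f | d = 5 | d = 10 | d = 20 |
|---|---|---|---|
| 10% | 0.5 | 1.0 | 2.0 |
| 20% | 1.0 | 2.0 | 4.0 |
| 30% | 1.5 | 3.0 | 6.0 |
| 50% | 2.5 | 5.0 | 10.0 |

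The bias equals the 1.3-point half-width when f = 1.3/d: 26% for d = 5, 13% for d = 10 and 6.5% for d = 20.

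**5. Size of the class I effect, if NYHA is judged at enrollment**

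Let q be the share of already-treated patients now in class I, with f here the already-treated share before any are turned away. The share of the group lost is f × q. For assumed f of 10% to 50% and q of 5% to 20%, this runs from 0.10 × 0.05 = 0.5% to 0.50 × 0.20 = 10%. If 30% were in class III/IV before first dose and all improvers came from class II (both assumed), the class III/IV share becomes 0.30/(1 − fq). That is 30.15% to 33.33%, a rise of 0.15 to 3.3 points. If improvers came from class III/IV instead, the share would fall, so even the direction is not fixed.

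**The case against.** A reader might infer that the protocol bars already-treated patients who have improved to class I, and that it fixes on-treatment values as their baseline. The text does not go that far. Criterion 3 has no date; among the clinical entry criteria only exclusion 4 is tied to the moment of enrollment. Judging current class is the natural reading, but it is a reading. The entry condition in 7.2.1 can mean pre-dose records, and 7.4 allows retrospective collection from medical records. The sentence in 7.4 that places baseline after consent and enrollment concerns only the two questionnaires. These points stand, and they make this an unreconciled index date, not a stated wrong rule.

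A reader might also infer that the NYHA filter works in one group only. It does not: SoC patients who reached class I on existing therapy are filtered too, and symptomatic CHF is the declared target population. What is particular to already-treated sacubitril/valsartan patients is that their values may postdate the decision under study.

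Some protection exists. Dose at initiation and titration steps are recorded, 7.7 plans subgrouping, 7.9 acknowledges the absence of temporal stipulations, and no follow-up data are compared between groups. An analysis plan could define subgroups. It could not supply pre-dose values that were never collected, so the reference date belongs in the protocol and the eCRF.

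**Conclusion.** The point holds as an unreconciled index date. Sections 7.1, 7.2.1, 7.2.2, 7.7 and 9 do not agree on the date to which the baseline profile and the NYHA criterion refer for patients already on sacubitril/valsartan. Followed as 7.1 is written, the time-varying part of their profile postdates the decision it is meant to explain. The demographic and etiological part of the first main objective is largely untouched.

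The size cannot be derived from the documents. The bias is f × d with both terms unknown. An already-treated share of 13% with a 10-point shift would match the stated ±1.3 points, but that is an illustration, not an estimate. The 50% row is a boundary case: enrollment opens in each country when the drug becomes available, and 7.2.1 expects slow early uptake. The class I loss of 0.5% to 10% rests on assumed shares and on the enrollment reading of criterion 3.

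**What to change.** Amend Sections 7.1 and 7.2.1 and Table 7-1, and clarify criterion 3 in 7.2.2:

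1. Record the date of first dose for every sacubitril/valsartan patient.
2. For patients already on drug at enrollment, take the time-varying variables of the first main objective from the last record before first dose, and anchor the event look-back at first dose. Record enrollment-visit values separately, labelled as on-treatment.
3. Report the first main objective and the change summaries (NYHA, BNP/NT-proBNP) separately for new starters and already-treated patients.
4. State the date to which criterion 3 refers, reconciling 7.2.1 with 7.2.2, without otherwise changing eligibility. Moving the NYHA test to before first dose would admit currently asymptomatic patients in one group only, and is not needed to cure the profile problem.

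The cost is a few more eCRF fields and tables, and some missing pre-dose values. The burden is modest, because 7.2.1 already makes baseline information on file a condition of entry and 7.4 allows retrospective collection.
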